#### 6.4.1. Definition of Other Secondary Efficacy Endpoints

##### 6.4.1.1. ACR50 and ACR70

ACR50 and ACR70 are similarly defined as ACR20 (see Section 6.2.1), except the improvement threshold from Baseline is 50% and 70%, respectively.

##### 6.4.1.2. SDAI and CDAI

Simplified Disease Activity Index (SDAI) is a composite measure that sums the TJC28, SJC28, the SGA on a 0-10 scale, the PGA on a 0-10 scale, and the CRP (in mg/dL). SDAI is scored as follows {Aletaha 2005}:

$$\text{SDAI} = \text{TJC28} + \text{SJC28} + \text{SGA} + \text{PGA} + \text{CRP}$$

Higher SDAI score indicates more severe disease activity status.

Clinical Disease Activity Index (CDAI) is a further simplification of the SDAI that excludes the CRP, which is calculated using the following formula {Aletaha 2005}:

$$\text{CDAI} = \text{TJC28} + \text{SJC28} + \text{SGA} + \text{PGA}$$

CDAI can range from 0 to 76, with higher score indicating more severe disease activity status.

No component-level imputation will be performed for the calculation of both SDAI and CDAI. If any components are missing, the SDAI and CDAI will be set as missing.

##### 6.4.1.3. ACR-N

ACR-N is defined as the smallest percentage improvement from baseline in swollen joints, tender joints and the median of the following 5 items (PGA, SGA, subject's pain assessment, HAQ-DI and CRP). It has a range between 0 and 100%. In particular,

ACR-N = min { improvement in TJC68 (%), improvement in SJC66 (%), median [improvement in SGA (%), improvement in PGA (%), improvement in pain assessment (%), improvement in HAQ-DI (%), improvement in hsCRP (%)] }.

If this calculation results in a negative value, then the ACR-N is set to 0. If any components are missing, the ACR-N will be set as missing.

#### 6.4.1.4. EULAR Response

Subject’s response will be categorized according to the following table based on the DAS28(CRP).

**Table 6-2. EULAR Response Criteria**

DAS28(CRP) at Visit	DAS28(CRP) Improvement from Baseline		
	> 1.2	> 0.6 and ≤ 1.2	≤ 0.6
≤ 3.2	Good Response	Moderate Response	No Response
> 3.2 and ≤ 5.1	Moderate Response	Moderate Response	No Response
> 5.1	Moderate Response	No Response	No Response

#### 6.4.1.5. European Quality of Life 5 Dimensions – 5 Levels (EQ-5D-5L)

The EQ-5D-5L is a standardized measure of health status of the subject at the visit (same day) that provides a simple, generic measure of health for clinical and economic appraisal. The EQ-5D-5L consists of 2 components: a descriptive system of the subject’s health and a rating of his or her current health state using a 0 to 100 VAS. The descriptive system comprises the following 5 dimensions: mobility, self-care, usual activities, pain/discomfort, and anxiety/depression. Each dimension has 5 levels: no problems, slight problems, moderate problems, severe problems, and extreme problems. The subject is asked to indicate his/her health state by ticking (or placing a cross) in the box associated with the most appropriate statement in each of the 5 dimensions. The VAS records the subject’s self-rated health on a vertical VAS in which the endpoints are labeled “best imaginable health state” on the top and “worst imaginable health state” on the bottom. Higher EQ VAS indicates better health. The EQ-5D-5L will be scored according to the developer’s instructions (scoring guidelines).

#### 6.4.1.6. Work Productivity and Activity Impairment Questionnaire (WPAI) – RA

The WPAI is a questionnaire developed to measure impairments in work activities in subjects with RA. The questionnaire consists of 6 questions:

- Q1: currently employed,
- Q2: work time missed due to RA,
- Q3: work time missed due to other reasons,

- Q4: hours actually worked,
- Q5: degree RA affected productivity while working (0-10 VAS; with 0 indicating no effect and 10 indicating RA completely prevented the subject from working),
- Q6: degree RA affected productivity in regular unpaid activities (0-10 VAS; with 0 indicating no effect and 10 indicating RA completely prevented the subject’s daily activities).

The recall period for questions 2 to 6 is 7 days.

WPAI-RA outcomes are expressed as impairment percentages, with higher numbers indicating greater impairment and less productivity, that is, worse outcomes, as follows:

- Absenteeism (work time missed) due to RA:  $100 \times \{Q2/(Q2+Q4)\}$
- Presenteeism (impairment while working) due to RA:  $100 \times \{Q5/10\}$
- Work productivity loss (overall work impairment) due to RA:  $100 \times \{Q2/(Q2+Q4) + [(1-Q2/(Q2+Q4)) \times (Q5/10)]\}$
- Activity impairment due to RA:  $100 \times \{Q6/10\}$ .

If Question 1 (Are you currently employed?) is ‘NO’, then only the activity impairment score can be determined.

#### 6.4.1.7. Healthcare Resource Utilization Questionnaire

The Healthcare Resource Utilization Questionnaire (HRUQ) is designed to assess healthcare usage during the previous three months across a number of direct medical cost domains.

#### 6.4.1.8. Treatment Satisfaction Questionnaire for Medication (TSQM)

TSQM Scale scores are computed by adding the items loading on each factor. The lowest possible score is subtracted from this composite score and divided by the greatest possible score minus the lowest possible score. This provides a transformed score between 0 and 1 that should be multiplied by 100. Note that only one item may be missing from each scale before the subscale should be considered invalid for that respondent. Detailed scoring method is available in the Quintiles TSQM Scoring Manual v1.4.

CCI

#### **6.4.2. Analysis Methods for Other Secondary Efficacy Endpoints**

The FAS will be used for all summaries and analyses of other secondary efficacy endpoints. Nominal p-values will be presented, if applicable.

The proportion of subjects who achieve ACR20/50/70 and proportion of subjects with change in HAQ-DI  $\geq 0.22$  (ie, reduction in HAQ-DI  $\geq 0.22$ ), DAS28(CRP)  $\leq 3.2$ , and DAS28(CRP)  $< 2.6$  will be analyzed using the the same logistic regression method with NRI as the primary endpoint analysis described in Section 6.2.3. The 2-sided 95% CIs for the proportion based on normal approximation will be provided for each treatment group. The OC and LOCF values will be analyzed as a sensitivity approach to the primary method that uses NRI.

The proportion of subjects having no radiographic progression at Week 24 and 52 will be analyzed using the same logistic regression method based on the OC. Comparison will be made between each filgotinib dose group and MTX alone group. The 2-sided 95% CIs for the proportion based on normal approximation will be provided for each treatment group. In addition, similar analysis will be performed with thresholds of 0 and the smallest detectable change (SDC). The change from Baseline in mTSS, DAS28(CRP), CDAI and SDAI will be analyzed using MMRM method that include all available data at postbaseline visits through Week 52. The MMRM models will include baseline value, stratification factors, treatment, visit, and treatment by visit interaction included as fixed effects and subject being the random effect. An unstructured variance-covariance matrix will be used. The Kenward-Roger method will be used to estimate the degrees of freedom. Missing change scores due to missing study visits or early withdrawal will not be otherwise imputed using the MMRM approach. The LS means along with 95% CIs of the difference in mean change scores from Baseline between each filgotinib dose group and MTX alone group from the MMRM model will be provided for each postbaseline visit. Descriptive statistics of actual and change in DAS28(CRP), CDAI, SDAI, and mTSS from baseline to postbaseline visits will also be performed by treatment and visit.

Actual values and change from Baseline in individual components of the ACR response (including TJC68, SJC66, SGA, PGA, Subject's pain assessment, and hsCRP), TJC 28, SJC28, and ACR-N will be summarized using descriptive statistics (sample size, mean, SD, median, Q1, Q3, minimum, and maximum) by treatment and visit. In addition, the MMRM model with baseline value, stratification factors, treatment, visit, and treatment and visit interaction as fixed effects and subject being the random effect will be performed to compare each filgotinib dose group and MTX alone group. The LS means and 95% CI of the difference between each filgotinib dose group and MTX alone group will be provided.

Actual values and change from Baseline in ACR-N will be summarized using descriptive statistics (sample size, mean, SD, median, Q1, Q3, minimum, and maximum) by treatment and visit.

Number and percentage of subjects for EULAR responses will be presented for each visit through Week 52 by treatment.

For HRQoL endpoints, the analysis methods are detailed below:

- **SF-36**

The transformed scores and change from baseline in the 8 domains and 2 summary component scores (PCS and MCS) of the SF-36 will be summarized at each visits through Week 52 by treatment group using descriptive statistics (sample size, mean, SD, median, Q1, Q3, minimum and maximum).

The change from Baseline in PCS and MCS at each postbaseline visit through Week 52 will be analyzed using MMRM method that includes all available data at postbaseline visits, without imputation for missing data. The MMRM models will be used to evaluate treatment effect on change score from Baseline, with baseline value, stratification factors, treatment, visit, and treatment by visit interaction included as fixed effects and subject being the random effect. An unstructured variance-covariance matrix will be used. The Kenward-Roger method will be used to estimate the degrees of freedom. To test for a treatment difference between each filgotinib dose group and MTX alone group, the LS means along with the 95% CIs of the difference and p-value from MMRM will be provided for each postbaseline visit.

- **FACIT-Fatigue**

The change from baseline in FACIT-Fatigue scale score at each postbaseline visit through Week 52 will be analyzed using similar MMRM models as for SF-36. To test for a treatment difference between each filgotinib dose group and placebo, LS mean difference along with 95% CI and p-values will be presented for each postbaseline visit. Missing change scores due to missing study visits or early withdrawal will not be otherwise imputed using the MMRM approach. Summary statistics of the actual score and change from baseline in FACIT-Fatigue scale score will also be displayed by treatment and visit.

- **EQ-5D-5L**

Summary statistics of two outcomes of the EQ-5D-5L described as the following will be provided:

- A health profile: the number and percentage of subjects at each categorical response for the 5 dimensions (mobility, self-care, usual activity, pain/discomfort, and anxiety/depression) will be provided by treatment and visit.
- A self-perceived current health score: calculated from patient level EQ VAS responses (continuous variable). Descriptive statistics (sample size, mean, SD, min, median, and max) will be provided by treatment and visit.

The change from baseline in EQ VAS score through Week 52 will be analyzed using similar MMRM models as for SF-36. To test for a treatment difference between each filgotinib dose group and placebo, LS mean difference, 95% CI and p-values will be presented. Missing change scores due to missing study visits or early withdrawal will not be otherwise imputed using the MMRM approach.

- **WPAI – RA**

Summary statistics of the actual scores and change from baseline in each of the four types of scores of WPAI-RA (absenteeism, presenteeism, work productivity loss, and activity impairment) will be summarized by treatment and visit using descriptive statistics (sample size, mean, SD, median, Q1, Q3, minimum and maximum).

The analyses of absenteeism, presenteeism, and work productivity loss will be based on subjects employed at both baseline and postbaseline visits.

- **HRUQ**

Summary statistics will be provided for all the following parameters by treatment group and visit.

*Healthcare resource utilization – Outpatient visits:*

— Number and percentage of subjects with any medical visits, and the number of visits related to RA will be provided for the categories:

- Outpatient Healthcare Provider
- Emergency Room
- Chiropractor, Physical or Occupational Therapist

*Healthcare resource utilization – Inpatient hospitalization:*

— Number and percentage of subject with hospital stays, and number of stays related to RA

— Descriptive statistics for the total number of days in hospital related to RA

— Number and percentage of subject with nursing home or rehabilitation center stays, and number of stays related to RA

— Descriptive statistics for the total number of days in nursing home or rehabilitation center related to RA

- **TSQM**

Descriptive statistics of the scores from each of the 4 domains (Effectiveness, Side-Effects, Convenience, and Global Satisfaction) will be presented by treatment group and by visit.

[REDACTED]

Plots of proportions of subjects for categorical endpoints and mean  $\pm$  SD for continuous endpoints (including each individual component of the ACR response) will be presented over time by treatment.

In addition, all available data including those collected under the standard of care will be summarized by treatment group for the proportion of subjects who achieve ACR20, DAS28(CRP)  $\leq$  3.2, and DAS28(CRP)  $<$  2.6, and the actual value and change from Baseline in HAQ-DI, mTSS, SF-36 PCS score, and FACIT-Fatigue. The observed values will be analyzed, and no formal statistical testing will be performed.

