### **3. GENERAL CONSIDERATIONS FOR DATA ANALYSES**

Analysis results will be presented using descriptive statistics. For categorical variables, the number and percentage of subjects in each category will be presented; for continuous variables, the number of subjects (n), mean, standard deviation (SD) or standard error (SE), median, first quartile (Q1), third quartile (Q3), minimum, and maximum will be presented.

All statistical tests will be 2-sided and performed at the 5% significance level unless otherwise specified.

By-subject listings will be presented for all subjects in the All Randomized Analysis Set and sorted by subject identification (ID) number, visit date, and time (if applicable). Data collected on log forms, such as AEs, will be presented in chronological order within the subject. The treatment group to which subjects were randomized will be included in the listings, as well as age, sex at birth, race, and ethnicity.

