### **6.2.3. Primary Analysis of the Primary Efficacy Endpoint**

To test for superiority of filgotinib 200 mg in combination with MTX group versus MTX alone group in proportion of subjects who achieve ACR20 at Week 24, a logistic regression analysis with treatment groups and stratification factors in the model will be used. Subjects who do not have sufficient measurements to establish efficacy at Week 24 will be considered as failures (ie, NRI). The p-value from the logistic regression model for testing the superiority of filgotinib 200 mg in combination with MTX as compared to MTX alone will be provided. The 2-sided 95% confidence interval (CI) of the ACR20 response rate at Week 24 based on normal approximation for each treatment group will be provided for each treatment group. In addition, non-stratified ACR20 response rate difference between treatment groups with its 95% CI based on the normal approximation will be provided.

The comparisons of other filgotinib dose groups versus MTX alone group in proportion of subjects achieving ACR20 at Week 24 will also be conducted with the similar logistic regression model with NRI.

The number and percentage of ACR20 nonresponders observed and nonresponders due to missing at Week 24 will be summarized respectively by treatment groups.

For subjects with observed ACR20 outcomes (ie, responders and observed nonresponders) at Week 24, actual values and change from Baseline at Week 24 in individual components, including TJC68, SJC66, SGA, PGA, Subject's Pain Assessment, and hsCRP, will be summarized by using descriptive statistics (sample size, mean, SD, median, Q1, Q3, minimum, and maximum) by treatment groups.

The proportions of subjects achieving ACR20 (using NRI) will be plotted over time by treatment.

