#### **6.4. Other Secondary Efficacy Endpoints**

Other secondary efficacy endpoints include:

- Change from Baseline in the mTSS at Week 52
- The proportion of subjects who achieve ACR50 and ACR70 at Weeks 4, 12, 24, and 52, ACR20 at Weeks 4, 12, and 52, and ACR20/50/70 over time from Day 1 through Week 52
- Change from Baseline in individual components of the ACR response at Weeks 4, 12 and 24, and 52 and over time from Day 1 through Week 52
- The proportion of subjects who achieve change (ie, decrease) in HAQ-DI of  $\geq 0.22$  at Weeks 4, 12, 24, and 52, and over time from Day 1 through Week 52
- Change from Baseline in DAS28(CRP) at Weeks 4, 12, 24, and 52, and over time from Day 1 through Week 52
- The proportion of subjects who achieve DAS28(CRP)  $\leq 3.2$  at Weeks 4, 12, 24, and 52, and over time from Day 1 through Week 52
- The proportion of subjects who achieve DAS28(CRP) < 2.6 at Weeks 4, 12, and 52, and over time from Day 1 through Week 52
- ACR-N and European League Against Rheumatism (EULAR) response at Weeks 4, 12, 24 and 52, and over time from Day 1 through Week 52
- Change from Baseline in CDAI at Weeks 4, 12, 24, and 52, and over time from Day 1 through Week 52

- Change from Baseline in SDAI at Weeks 4, 12, 24, and 52, and over time from Day 1 through Week 52
- The proportion of subjects who had no radiographic progression from Baseline (applying threshold of 0.5 on change from baseline in mTSS) at Week 24 and 52
- Absolute value and change from Baseline in SF-36, FACIT-Fatigue, and the EQ-5D over time at Weeks 4, 12, 24, and 52, and over time from Day 1 through Week 52
- Absolute value and change from Baseline in WPAI-RA at Weeks 4, 12, 24, and 52, and over time from Day 1 through Week 52

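### SAP 6.4.2 sets Wald intervals and a logistic test for strict response endpoints from the first visits, with no rule for zero or very small responder counts

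*SAP*

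**What the plan says.** SAP 6.4.2 analyses ACR20/50/70, the HAQ-DI reduction of at least 0.22, DAS28(CRP) ≤ 3.2 and DAS28(CRP) < 2.6 with the same "logistic regression method with NRI as the primary endpoint analysis described in Section 6.2.3". For the rates themselves: "The 2-sided 95% CIs for the proportion based on normal approximation will be provided for each treatment group". SAP 6.2.3 describes the model only as "a logistic regression analysis with treatment groups and stratification factors in the model will be used"; it does not say whether the p-value is Wald, likelihood-ratio or score.

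SAP 6.4 sets the timing. It lists "ACR20/50/70 over time from Day 1 through Week 52", and DAS28(CRP) < 2.6 "at Weeks 4, 12, and 52, and over time from Day 1 through Week 52". The first post-baseline analysis window in SAP Table 3-1 is Week 2.

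On inferential status, SAP 6.4.2 says: "Nominal p-values will be presented, if applicable". SAP 6.4.2 gives no fallback for sparse counts. Fisher's exact test appears only for subgroups (SAP 6.2.5 and 6.3.4).

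**The concern.** A normal-approximation interval and a logistic test suit ACR20 at Week 24, where the planning rates are 62% and 78%. SAP 6.4.2 carries the same tools to ACR70 or DAS28(CRP) < 2.6 at Weeks 2 and 4. At those visits MTX has only been given at its 10 mg starting dose (Protocol 5.3.4; the first increase is at the Week 4 visit), so responders could be very few.

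With few responders the Wald interval is too short or impossible. With none in a compared arm, the maximum-likelihood treatment effect is infinite and a Wald p-value carries no information. SAP 6.5 replaced the Cochran-Mantel-Haenszel test with logistic regression because some strata are small. The replaced test still gives a usable p-value when one arm is empty, whereas a Wald logistic test does not. At stake is whether the early-visit tables show credible intervals and p-values.

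**Working it through.** **Inputs.** Arm sizes are 400 (filgotinib 200 mg + MTX), 200, 200 and 400 (MTX alone), from SAP 1.3. Non-responder imputation (SAP 6.1) keeps denominators at full arm size. The plan gives no figure for early intervals or p-values. Its nearest figure, 90% power for mTSS with 400 per arm, reproduces: √(400/2) × 0.62/2.7 − 1.96 = 1.29, which is 90.1% power.

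**Assumed.** The true early response rate is varied from 0.25% to 2%. The lowest control rate in the documents is placebo ACR70 at Week 12, 2/72 = 2.8% (Protocol Table 1-2).

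**1. Wald limits.** The interval is p̂ ± 1.96 √(p̂(1 − p̂)/n). The lower limit is negative when p̂ < z²/(n + z²). For n = 400 that is 3.84/403.84 = 0.95%, so 3 responders or fewer.
- 0/400: 0% to 0% (Wilson 0% to 0.95%)
- 1/400: 0.25% ± 0.49%, so −0.24% to 0.74% (Wilson 0.04% to 1.40%)
- 4/400: 1.00% ± 0.98%, so 0.03% to 1.98%

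**2. Exact coverage, n = 400.** Coverage is the sum of binomial probabilities over the counts whose interval contains the true rate.

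| True rate | P(0 responders) | P(0-3) | Wald coverage | Wilson coverage |
|---|---|---|---|---|
| 0.25% | 36.7% | 98% | 63.2% | 92.0% |
| 0.5% | 13.5% | 86% | 86.4% | 94.8% |
| 1% | 1.8% | 43% | 90.7% | 93.2% |
| 2% | 0.03% | 4.1% | 89.5% | 95.4% |

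The shortfall can be traced by hand. At 0.5%, the 13.6% miss is almost all P(0) = 0.995^400 = 13.5%. At 1%, counts of 0 and 1 give upper limits below 1%, and P(X ≤ 1) = 0.01795 × (1 + 4/0.99) = 9.0% of the 9.3% miss.

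**3. p-value with an empty arm, 0/400 versus 8/400.**
- Wald: the fit stops at a log odds ratio of 22.67 with SE about 17,800, so z ≈ 0.001 and p = 0.999.
- Likelihood ratio, same model: G² = 2[8 ln(8/4) + 392 ln(392/396) + 400 ln(400/396)] = 2(5.545 − 3.980 + 4.020) = 11.17, p = 0.0008.
- Fisher: p = 0.0075.

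The Wald p stays at 0.999 for 16/400 and 32/400 against 0/400. It also stays near 1 for all three comparisons in a four-arm model with simulated region and serostatus strata and no MTX responders.

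**4. One responder, 1/400 versus 8/400.** The log odds ratio is ln[(8/392)/(1/399)] = 2.10 and SE = √(1/8 + 1/392 + 1 + 1/399) = 1.06, so Wald p = 0.049 (likelihood ratio 0.012, Fisher 0.038). The breakdown is gone.

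**5. At the primary endpoint's planning rate, 62% of 400.** Wald gives 57.24% to 66.76% and Wilson gives 57.15% to 66.62%. The choice hardly matters there.

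**The case against.** The strongest reply is that low early MTX rates are not documented. The 10 mg start makes them plausible but supplies no number. At the lowest control rate shown, 2.8%, the chance of 0 responders in 400 is about 0.001%, the chance of 0-3 is 0.4%, and Wald coverage is about 92%. The empty-arm failure also needs a Wald statistic, which the SAP does not name. The p-values are nominal, and a reader who sees 0/400 beside 8/400 would recognise a degenerate result. All of this stands, and it limits the point. It does not remove the under-coverage at 1-2%, nor the absence of any rule.

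A reader might infer more than the documents support:
- *That the methods fail at every visit.* They apply at every visit; the damage is confined to the earliest visits and strictest endpoints.
- *That low rates alone drive p towards 1.* This requires exactly zero responders in a compared arm and a Wald test.
- *That MTX coverage falls to 63% at a true rate of 0.5%.* That figure belongs to n = 200, and both 200-subject arms receive filgotinib. The documents do not suggest filgotinib rates that low, and Protocol 1.2.3 reports ACR50 responses from Week 2 in phase 2.
- *That the main conclusions are at risk.* Nothing shows the primary or hierarchical Week 24 tests to be affected, and no unredacted objective concerns onset of action.

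**Conclusion.** The point holds as a limited, inexpensive improvement to a stated method. If true early rates are about 2% or less, nominal 95% intervals in a 400-subject arm cover about 86-91% of the time for rates of 0.5% to 2%, against 93-95% for Wilson, and some printed limits will be impossible. Those rates are an assumption. The p-value failure is total when it occurs but has two conditions: an empty compared arm and a Wald statistic. At a true 1% rate, the chance of an empty 400-subject arm is only 1.8%. The consequence is for the reporting of nominal, early-visit results and not for the confirmatory conclusions.

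**What to change.** In SAP 6.4.2, replace the normal-approximation intervals for response proportions with Wilson intervals. Add that, when any arm in a comparison has zero responders, the p-value comes from a likelihood-ratio or Firth-penalised logistic test, or from a Fisher or stratified exact test. Name one of these before unblinding. SAP 6.2.3 needs no change.

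The cost is two sentences and standard software options. The downside is that the intervals are no longer symmetric about the observed rate.
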